1.0 STUDY SYNOPSIS

Name of Sponsor:	Nektar Therapeutics
Name of Finished Product:	NKTR-181 tablets
Name of Active Ingredient:	NKTR-181
Title of Study:	A Phase 3 Multicenter, Open-Label, 52-Week Study to Evaluate the Long-Term Safety and Tolerability of NKTR-181 in Subjects with Moderate to Severe Chronic Low Back Pain or Chronic Noncancer Pain
Duration of Study:	Approximately 57 weeks for each subject
Phase of Development:	3
Objectives:	
Primary:
 
 To evaluate the long-term safety and tolerability of NKTR-181 in subjects with moderate to severe chronic low back pain or chronic noncancer pain. 
Secondary:
 
 To evaluate the efficacy of NKTR-181 as measured by the modified Brief Pain Inventory-Short Form (mBPI-SF).
Study Population	Opioid non-tolerant adults 18-75 years of age, inclusive, with moderate to severe chronic low back pain or chronic noncancer pain.
Number of Subjects (planned):	Approximately 600 subjects are expected to be enrolled. This number may increase or decrease to meet the International Conference on Harmonisation (ICH) regulatory exposure requirements for NKTR-181 of at least 300 subjects who complete 26 weeks of NKTR-181 treatment and at least 100 subjects who complete 52 weeks of NKTR-181 treatment. The subjects will comprise those qualifying to rollover from completing Study 14-181-07 and Study 14-181-12 as well as newly enrolled (“De Novo”) subjects qualifying for this study. Approximately 250 De Novo Subjects will be enrolled in the trial.
Number of Study Sites:	Approximately 100
Countries:	USA
Key Inclusion Criteria:	
 Clinical diagnosis of moderate to severe chronic low back pain for > 3 months before signing the informed consent form (ICF). Newly enrolled subjects (“De Novo Subjects”) who are treating their chronic low back pain with no less than 10 mg but no more than 60 mg of morphine sulfate equivalents/day for at least the 7 days prior to signing the ICF.. Subjects who have completed Study 14-181-07 or Study 14-181-12 and meet entry criteria are eligible (“Rollover Subjects”).
Study Design:	
Open-label, multicenter, safety and tolerability study of NKTR-181 in the treatment of moderate to severe chronic low back pain or chronic noncancer pain.
 
The study will be divided into the following 3 periods:
 
 Screening: Up to 21 days Treatment: Up to 52 weeks (inclusive of a 1-week taper) Follow-up: Approximately 14 days after last dose of study drug

Test Product, Dose and Mode of Administration:	
Name: NKTR-181 tablet(s)
 
Dose, Route, and Frequency: NKTR-181 100-mg and 200-mg tablets will be administered orally twice daily (BID) as doses of 100 mg, 200 mg, 300 mg, 400 mg, 500 mg and 600 mg BID. Each dose will consist of tablets as follows:
 
100-mg dose = 1 x 100-mg tablet
 
200-mg dose = 1 x 200-mg tablet
 
300-mg dose = 1 x 200-mg tablet + 1 x 100-mg tablet
 
400-mg dose = 2 x 200-mg tablets
 
500-mg dose = 2 x 200-mg tablet + 1x 100-mg tablet
 
600-mg dose = 3 x 200 mg tablet
 
Subjects should take NKTR-181 BID at approximately 8 AM and 8 PM.

Safety:	
Key Safety Endpoints:
 
Safety and tolerability will be evaluated based on the following:
 
 • Incidence, type, seriousness, and severity of adverse events (AEs) reported • Clinical laboratory evaluations • Electrocardiograms (ECGs) • Vital signs (respiratory rate, pulse, heart rate, blood pressure, and temperature) • Drug withdrawal as measured by the Clinical Opiate Withdrawal Scale (COWS) and the Subjective Opiate Withdrawal Scale (SOWS) • Incidence of aberrant drug behavior according to MADDERS™ assessment • Suicidality assessment (Columbia-Suicide Severity Rating Scale [C-SSRS])
Efficacy:	
Efficacy Endpoint:
 
 • Efficacy will be evaluated based on the mBPI-SF administered at clinic visits.
Pharmacokinetics:	
Plasma concentrations of NKTR-181 and selected metabolites will be tabulated by time and subject and assessed for relationship to dose during the treatment phase. These data will be pooled with those from other studies during population PK analyses and investigation of exposure-response relationships for efficacy and safety.

Statistical Methods:	
Summaries for the assessment of long-term safety will be presented by De Novo and Rollover Subjects separately and for all subjects combined. The frequency and percentage of subjects experiencing treatment-emergent adverse events (TEAEs), serious adverse events (SAEs), and AEs leading to withdrawal from the study drug will be tabulated by Medical Dictionary for Regulatory Activities (MedDRA) system organ class, preferred term, severity, and relationship to the study drug. Laboratory test results, vital signs, ECGs, SOWS, COWS, and change from baseline will be summarized using descriptive statistics. The relationship between duration of exposure and the frequency and severity of AEs will be examined. Time-to-event endpoints will be estimated using the Kaplan-Meier method. Change over time from baseline in each question and metric of the mBPI-SF will be summarized using descriptive statistics.

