5.3 Removal of Subjects from Study Therapy or Assessment

Subjects may choose to discontinue the study at any time, for any reason, and without prejudice to further treatment.

Subjects may stop participating in or be withdrawn from the study for any of the following reasons but are to be followed for safety until resolution or for 14 days after the subject's last study visit, whichever comes first (see Section 10.1.5):

- Lack of efficacy
- Occurrence of an unacceptable AE
- Opioid withdrawal
- Noncompliance of the subject with protocol-mandated procedures
- Continued participation is no longer in the subject's best interest in the opinion of the Investigator
- The subject is lost to follow-up. Before a subject is considered "lost to follow-up," study personnel must contact the subject at least twice by phone and once by mail with documented receipt(s)
- Death
- The study is terminated by the sponsor

During the treatment period, if an ECG is obtained and reveals that the subject's QTcF interval is > 500 msec or has an increase of ≥ 60 msec compared to baseline QTcF and confirmed with a second ECG within 30 minutes, treatment with study medication should be interrupted. In the event this occurs, the investigator should contact the Medical Monitor as soon as possible to discuss if the subject can continue on treatment or if the subject should stop study medication.

In the event of a subject's withdrawal, the Investigator will promptly notify the sponsor and make every effort to complete the ET assessments specified in the Schedule of Assessments (Section 1.2).

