Subjects will return to the clinic for assessments of tolerability and effectiveness every 4 to 10 days for up to 6 more times over a 5-week period until a stable dose is achieved. A **stable** dose is a dose that is effective and tolerated on two sequential visits (i.e., after at least 8 days of continuous treatment). Subjects who continue to tolerate study drug but do not have adequate relief of pain, based on the Investigator's clinical judgment, will continue dose escalations of 100-mg BID increments until the maximum dose of 600-mg NKTR-181 BID is reached.

Subjects who do not achieve adequate pain control at 600-mg NKTR-181 BID will be classified as non-responders and will be discontinued from further participation in the study.

Non-responders will be required to complete the ET Visit (Visit 21/ET) and safety follow-up requirements.

Subjects will begin a monthly clinic visit schedule after a tolerable, effective and stable dose is achieved. **Doses of NKTR-181 may be adjusted upwards (up to a maximum dose of 600-mg NKTR-181 BID) or downwards as needed during the Treatment Period, based on the Investigator's (or qualified sub-Investigator's) assessment of effectiveness and tolerability.**

If at any time a subject cannot tolerate study drug between protocol-mandated visits, per Investigator discretion, an unscheduled visit should occur. For subjects with tolerability issues, the dose of NKTR-181 may be adjusted downwards, as necessary, based on the Investigator's clinical judgment in a stepwise 100-mg changes (e.g., 300-mg BID may be lowered to 200-mg BID). Dose adjustments may occur at unscheduled visits, however, an unscheduled visit will not replace a regularly scheduled visit, and the subject should be seen at all regularly scheduled visits.

Throughout the Treatment Period, subjects who experience breakthrough pain will be allowed rescue medication, as outlined in Section 6.4. Note: If subject is off of study drug for 3 days or more, sponsor **must** be consulted prior to restarting study drug.

Subjects will report their pain experience at each visit using the mBPI-SF. At quarterly intervals, subjects will be assessed for vital signs, 12-lead electrocardiogram (ECG), and clinical laboratory testing.

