11.10 Efficacy Analyses

11.10.1 Modified Brief Pain Inventory–Short Form

The mBPI-SF will be assessed at each visit during the study. The change from baseline and value at each visit will be summarized descriptively over time.

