11.11 Missing Data

Missing data will not be imputed. Final statistical considerations and methodology for handling missing data will be detailed in a separate document (SAP).

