8.6 Efficacy Endpoint

The mBPI-SF will be assessed at each visit during the study. The mean of the 4 intensity items (3-6) will be calculated and used as a measure of pain severity. The mean of the 7 interference items (9A-9G) will be calculated and used as a measure of Pain interference. Change from baseline to each month (visit) will be calculated for the Pain severity, Pain interference, and each individual score, if applicable.

If there are missing items when the pain severity score and pain interference score are calculated, the mean of the completed items in one dimension (dimensions include pain severity and pain interference) will be imputed to substitute the missing item, provided that more than 50% of the items in one dimension are completed ([Halling, 1999](#)).

The change from baseline and value for mBPI-SF dimensions and individual scores at each visit will be summarized descriptively over time.

In addition, an exploratory analysis will be performed on mBPI. The change from baseline to the end of the long term safety study will be analyzed. Baseline will be considered as last non-missing assessment on or prior to the first dose in this long term safety study (visit 3). The change from baseline will be analyzed using Mixed Model Repeated Measure (MMRM) analysis. The model will include change from baseline as dependent variable, baseline score as a covariate, subject's status (De Novo or Rollover with NKTR-181 or Rollover with Placebo), time, subject's status and time interaction as fixed effects. Point estimates on the Least Squared means over time will be calculated with corresponding 95% confidence intervals different dose levels. These analysis will be applied to both pain intensity and interference based on mBPI. The pain intensity means and LSmeans over time will be present graphically.

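### By-visit mBPI-SF means are taken on subjects still in the study after outcome-related removal, and the SAP's safeguards leave gaps for pain interference, individual items and informative drop-out

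*Protocol*

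**What the plan says.** **Removal.** Protocol 6.2: "Subjects who do not achieve adequate pain control at 600-mg NKTR-181 BID will be classified as non-responders and will be discontinued". Protocol 5.3 also lists "Lack of efficacy" as a reason for withdrawal, with no limit on when it may apply.

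**Descriptive summary.** The synopsis states "Change over time from baseline in each question and metric of the mBPI-SF will be summarized using descriptive statistics", and Protocol 11.10.1 repeats the by-visit plan. SAP 8.6 keeps it: "The change from baseline and value for mBPI-SF dimensions and individual scores at each visit will be summarized descriptively over time".

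**Missing data.** Protocol 11.11 says "Missing data will not be imputed" but leaves the final method to the SAP. SAP 8.6 fills in missing items within a partly completed form when more than half of that dimension is answered. SAP 8.10 allows no imputation beyond what the SAP states. Nothing fills in a missing visit in the descriptive tables.

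**What the SAP adds.**
- 8.6: an exploratory MMRM on change from baseline, for both pain intensity and interference, with LS means and 95% confidence intervals over time.
- 8.6.1: responder rates for pain intensity over the whole analysis set, with discontinued or missing subjects counted as non-responders.
- 8.6.3: Kaplan-Meier time to discontinuation, with lack of efficacy shown separately.
- 8.1: reasons for discontinuation, by highest titrated dose.
- 7.1: n as a default descriptive statistic.

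**The concern.** Effectiveness on the mBPI-SF is the only secondary objective, and there is no control arm. When subjects leave because their pain is not controlled, the later means come from a group partly selected on the outcome. A mean that holds or deepens over 52 weeks could then reflect lasting effect, selection, or both, and the descriptive table cannot tell them apart. SAP 8.6 also plots observed pain-intensity means alongside the LS means, so the selected means will be prominent.

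The point concerns analysis and presentation only. It does not question the discontinuation rule.

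**Working it through.** **Plan's own figure.** There is none to reproduce. The documents give no SD, drop-out rate or effect size for the mBPI-SF. The only figures bearing on attrition are in Protocol 11.2: about 600 enrolled, at least 300 completing 26 weeks and at least 100 completing 52 weeks. These floors would tolerate 1 - 300/600 = 50% loss by week 26 and 1 - 100/600 = 83% by week 52. They are minimum requirements, not forecasts.

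**Step 1: shift in an observed-case mean.** Assume changes are normal with standard deviation SD, a fraction d leaves, and the variable that drives exit correlates rho with pain change. The mean change of those remaining then looks better by

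rho x SD x phi(z) / (1 - d), where z is the 1 - d normal quantile.

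Example: d = 20%, SD = 2.0, rho = 1. z = 0.842 and phi(z) = 0.280, so 0.280/0.80 = 0.350, and 0.350 x 2.0 = 0.70 points. With rho = 0.5 it is 0.35.

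Results in points, for rho 0.5 to 1.0:

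| SD of change | 10% leave | 20% | 30% | 50% |
|---|---|---|---|---|
| 1.5 | 0.15-0.29 | 0.26-0.52 | 0.37-0.75 | 0.60-1.20 |
| 2.0 | 0.19-0.39 | 0.35-0.70 | 0.50-0.99 | 0.80-1.60 |
| 2.5 | 0.24-0.49 | 0.44-0.87 | 0.62-1.24 | 1.00-1.99 |

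**Step 2: do the SAP's other analyses remove the shift?** A simulation used 60,000 subjects and 12 visits, with mean baseline 6.5 and mean score 5.0 at every later visit, so the true change is flat at -1.50. The between-subject SD was 1.5 and the within-subject SD 1.2. Baseline was 6.5 plus half the subject effect plus noise of SD 1. The implied SD of change is sqrt(0.25 x 1.5² + 1.2² + 1²) = 1.73. At each visit after the first, a subject scoring above 6 left with probability 5%, 15% or 30%. Exit depended either on the last recorded score (missing at random) or on the current, unrecorded score (informative). All these inputs are assumed.

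At the last visit:

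| Exit driven by | Exit probability | Retained | Observed-case mean | MMRM | 30% responders, observed only | 30% responders, drop-outs as non-responders |
|---|---|---|---|---|---|---|
| Last recorded score | 5% | 85% | -1.61 | -1.51 | 43% | 37% |
| | 15% | 66% | -1.80 | -1.50 | 48% | 32% |
| | 30% | 51% | -1.99 | -1.50 | 54% | 28% |
| Unrecorded score | 5% | 86% | -1.63 | -1.55 | 43% | 37% |
| | 15% | 66% | -1.83 | -1.64 | 49% | 33% |
| | 30% | 51% | -2.04 | -1.79 | 56% | 28% |

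At the first visit the observed-case mean was -1.50 and the responder rate 39%. The true responder rate at the last visit was 40%.

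- The observed-case mean drifts by 0.11 to 0.54 points although nothing changes.
- The MMRM is within 0.01 of the truth when exit follows recorded scores, but drifts by 0.05 to 0.29 when it follows an unrecorded one.
- Counting drop-outs as non-responders does not inflate the rate.

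**Step 3: cover by outcome.**

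| Outcome | Observed-case summary | MMRM | Drop-outs as non-responders | Informative drop-out sensitivity |
|---|---|---|---|---|
| Pain intensity | yes | yes | yes | no |
| Pain interference | yes | yes | no | no |
| Individual items | yes | no | no | no |

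**Step 4: is the exit score recorded?** As the schedule in Protocol 1.2 reads, mBPI-SF has no mark under Visit 21/ET, the visit required of early leavers. SAP Table 1 has an mBPI entry for Visit 21, and Protocol 6.2 and 11.10.1 speak of every visit. If the schedule governs, the score nearest to exit may be missing, and missing-at-random is harder to defend.

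**The case against.** The strongest reply is that the SAP already does much of what is needed. The MMRM covers both domains, so a reader who infers that interference is analysed only on subjects who remain goes further than the documents allow. Pain intensity has an all-subject responder rate. The number leaving for lack of efficacy is shown, and n appears in each summary. This stands, and it narrows the point to the empty cells in the cover table.

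A reader might also infer that the means will improve over time through selection alone. The documents do not support that. Protocol 6.2 places all dose escalations before Visit 10, so the removal rule would act mainly around titration and could give largely a one-off shift. The same section also allows later upward adjustment, and withdrawal for lack of efficacy continues, so drift is possible but its size is unknown. Exits for adverse events, noncompliance or loss to follow-up need not track pain, and the top of the range in Step 1 needs rho = 1.

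mBPI-SF is scheduled at the titration visits, so scores preceding removal are normally recorded. That supports missing-at-random in part. It does not settle the matter, because the model is labelled exploratory, names no covariance structure and has no sensitivity analysis.

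Finally, safety is the primary objective and the mBPI-SF analysis is mainly descriptive. That limits the consequence but does not remove the bias.

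**Conclusion.** The point holds in limited form. Removal depends partly on the outcome, the by-visit mBPI-SF means are observed-case, and their bias, if any, is likely to run toward improvement. The documents cannot fix its size. It is about 0.15 to 1.2 points if 10-30% leave, the SD of change is 1.5-2.5 and rho is 0.5-1.0, all assumed. It shrinks toward zero if exits are unrelated to pain. The MMRM and the intensity responder rate reduce the problem but leave three gaps: no all-subject rate for interference, only observed-case summaries for items, and no check on missing-at-random.

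The documents do not support saying that the displays are bound to show growing benefit. This is a worthwhile, inexpensive improvement to the SAP. It does not affect the primary safety objective.

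**What to change.** In SAP 8.6:

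1. Label the by-visit means as observed-case. At each visit show the baseline mean of the same subjects beside their change, and show means by final disposition (completed, lack of efficacy, adverse event, other).
2. Extend the 8.6.1 responder definition, with discontinued or missing subjects as non-responders, to pain interference. Present the rates beside the means. Which display leads is a matter of preference.
3. Add one informative-drop-out sensitivity analysis to the MMRM, for example delta-adjusted after discontinuation for lack of efficacy or adverse event, with the deltas stated in advance. Report it separately for De Novo, Rollover-placebo and Rollover-NKTR-181 subjects. Setting change to zero after exit for everyone would not serve. Under Protocol 5.1.1 and 6.1.1, Rollover Subjects enter without a treatment break, so the Visit 3 baseline of those from NKTR-181 is already on drug, and zero change does not mean no benefit for them.

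Also reconcile the Protocol 1.2 schedule with SAP Table 1 on mBPI-SF at Visit 21/ET.

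Cost: SAP wording and a few extra tables from data already collected. If reconciliation shows that mBPI-SF was not planned at early termination, collecting it would add one questionnaire at a visit already required. The reported improvement may be smaller.

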1.1 Study Schematic

1.2 Schedule of Assessments

Assessment Period	Screening Up to 21 days		Treatment* 52 weeks							Follow-Up 14 days		Unscheduled Visit
	1	2 ¹	3	4, 5, 6, 7, 8, 9 (Flexible)	10, 13, 17, & 20	11 & 12	14-16 & 18-19	21/ET ²	22/EOT	23	24/EOS	
Dayse	≤ 21 days prior to Visit 3		1	Every 4-10 Days after previous visit	Every 30 (- 3)	Every 30 (- 3)	Every 30 (- 3)	D357 (+ 3)	D364 (+ 3)	72 hours	14 (± 2)	
Written informed consent	X											
Inclusion/exclusion criteria	X	X	X									
Demographics ³	X											
PHQ-8 ⁴	X											
Medical history ⁵	X											
Alcohol breath test ⁶	X											
Physical examination ⁷	X											
Vital signs ⁸	X		X	X	X				X	X		X
12-lead electrocardiogram ⁹	X				X				X			X
Clinical laboratory tests ¹⁰	X		X	X	X	X		X	X	X	X	X
Pregnancy test ¹¹	X		X		X				X			X
Urine drug screen ¹²	X		X	X	X							
eC-SSRS ¹³	X		X		X			X	X			
Taper opioid analgesics ¹⁴		X										
Dose titration assessment				X								
mBPI-SF ¹⁵			X	X	X	X	X		X			X
COWS		X ¹⁶	X ¹⁶					X	X	X	X	X
SOWS ¹⁷		X						X	X	X	X	
PK blood sample collection			X ¹⁸	X ¹⁹	X	X		X	X			X
Discontinue current analgesics			X									
Dispense/review/collect/instruct study drug			X	X	X	X	X	X ²⁰	X ²¹			X
Opioid side effect training			X									
Abuse & diversion assessment				X	X	X	X		X			X
Concomitant medications ²²			←									X
Adverse events ²²			←									X

Abbreviations: ALP, alkaline phosphatase; ALT, alanine aminotransferase; AST, aspartate aminotransferase; BMI, body mass index, COWS, Clinical Opiate Withdrawal Scale; eC-SSRS, electronic Columbia–Suicide Severity Rating Scale; ECG, electrocardiogram, EOS, end of study; EOT, end of treatment; ET, early termination; mBPI-SF, modified Brief Pain Index-Short Form; MSE, morphine sulfate equivalent; NRS numerical rating scale; PHQ-8, Personal Health Questionnaire Depression Scale PK, pharmacokinetic; SOWS, Subjective Opiate Withdrawal Scale; TBL, total bilirubin.

* If at any time a subject does not tolerate study drug between protocol-mandated visits in the Treatment Period, per Investigator discretion, an unscheduled visit should occur.

FOOTNOTES:

1. There is no Visit 2 for Rollover Subjects.
2. If a subject was dosed with study drug and discontinues from the study before completing all of the scheduled assessments, then assessments for Visit 21/ET and all safety follow-up procedures should be completed for this subject.
3. Demographics include birth date, race/ethnicity, smoking status, height, weight, BMI, and sex at birth. For Rollover Subjects, all demographic information (except weight and BMI) will be carried forward from Study 14-181-07 or Study 14-181-12.
4. The Personal Health Questionnaire Depression Scale (PHQ-8) is a self-administered (i.e., the subject completes the scale) version of the Primary Care Evaluation of Mental Disorders for mood. Subjects who score 10 or greater are not eligible to participate in this study.
5. Medical history includes medication history, history of substance or opioid abuse, medical/surgical history and concurrent illnesses and will be collected for all subjects and noted as to whether the condition is active. All relevant medical history will be collected and carried forward for Rollover Subjects. Ongoing adverse events that occurred in Study 14-181-07 and Study 14-181-12 will continue to be followed for Rollover Subjects.
6. Subjects who have a positive alcohol breath test will not be eligible for participation in this study.
7. Physical examination, including all major organ systems (general, head, eyes, ears, mouth/throat, neck, heart, lungs, abdomen, lymph nodes, joints, extremities, integumentary, neurologic, and psychiatric) will be performed for all De Novo Subjects. Physical examinations will not be conducted on Rollover Subjects.
8. Vital signs (respiratory rate, blood pressure, pulse, and temperature) will be measured after subjects have been resting for at least 5 minutes.
9. Subjects must be resting quietly in the supine position for > 5 minutes prior to collection of 12-lead ECG. During the treatment period, if an ECG is obtained and reveals that the subject's QTcF interval is > 500 msec or has an increase of ≥ 60 msec compared to baseline QTcF and confirmed with a second ECG within 30 minutes, treatment with study medication should be interrupted. In the event this occurs, the investigator should contact the Medical Monitor as soon as possible to discuss if the subject can continue on treatment or if the subject should stop study medication. Subjects who are discontinued will be required to complete the ET Visit and all safety follow-up procedures.
10. Clinical laboratory tests will include hematology, chemistry, and urinalysis at Visits 1, 10, 13, 17, 20, 21, and 22. Clinical laboratory tests will include only ALT, AST, ALP, and TBL at all other visits indicated. Clinical laboratory tests will be collected at Visits 23 and 24 only if results from previous visits were abnormal and clinically significant. Conjugated bilirubin is required only at Visit 1.
11. Pregnancy tests are required only for females of childbearing potential. Serum pregnancy test is required at Visit 1 (sent to central laboratory). Urine pregnancy test is required for subsequent visits. A negative pregnancy test result must be obtained before the administration of the study drug.

12. Urine dipstick drug test to screen for amphetamines, cannabinoids, cocaine, and opioids. Urine drug screen at visits 1 and 3 is done for De Novo subjects only. Urine drug screen at visit 4 is done for Rollover subjects only. No urine drug screen will be conducted at visits 5, 6,7,8 and 9. Rollover Subjects will have urine collected for testing at central lab rather than being tested onsite. Opioids will not be tested for Rollover Subjects at Visits 1 and 3. De Novo Subjects on non-opioid analgesics at the time of Visit 1 must have a negative urine drug screen at Visit 1 and Visit 3. De Novo subjects on opioid analgesics at the time of Visit 1 must have a negative urine drug screen for all drugs except opioids. Dipstick urine drug screen tests will be provided by the sponsor.
13. The electronic Columbia-Suicide Severity Rating Scale (eC-SSRS) is a subject self-report rating scale (i.e., the subject completes the scale) to lifetime and study-defined suicidal ideation and to assess suicidal ideation and behaviors since the time of the last visit. Subjects who answered YES to Question 4 or Question 5 within the past 12 months of the Baseline/Screening version of the eC-SSRS (Visit 1) are not eligible to participate in this study
14. De Novo subjects taking opioid analgesics will begin to taper their opioids over the next 7-14 days. Subjects must be on ≤ 30 morphine sulfate equivalents (MSE)/day for at least 3 days before proceeding to Visit 3.
15. The modified Brief Pain Inventory-Short Form (mBPI-SF) is a subject self-report rating (i.e., the subject completes the rating inventory) of pain and the impact of that pain on daily function.
16. De Novo Subject undergoing opioid taper will have COWS administered at Visit 2. All subjects will be administered COWS at Visit 3. COWS score must be ≤ 12 to enter the Treatment Period.
17. De Novo Subjects taking opioid analgesics at Visit 2 will complete a SOWS assessment daily while tapering their opioids over the next 7-14 days. All subjects will complete the SOWS on the two days prior to Visit 21 and daily between Visits 21 and 22. Subjects will then complete the SOWS twice daily for three days following the last dose of study drug (i.e., following Visit 22), then daily for the remainder for the study (i.e., through Visit 24).
18. A PK sample will be collected on all subjects at Visit 3. PK sample at Visit 3 must be collected prior to the subject taking the first dose of study medication for De Novo Subjects.
19. For subjects participating in the PK substudy, the dosing period PK collection may be completed when a stable dose has been identified. This may occur as early as the second visit following the start of a dose level. Subjects will be reminded to *not* take their AM dose on the planned dosing period PK collection visit. A predose sample will be obtained and the subject will take their AM dose in the clinic. PK samples will be obtained 0.5, 1, 2, 3, 4, 5, 6, 8, and 12 hours postdose.
20. Dispense taper study drug only for subjects completing study. Taper study drugs are not dispensed at Early Termination.
21. Study drug is not dispensed at Visit 22/EOT. Final study drug and rescue medication reconciliation conducted at Visit 22/EOT.
22. Collection of concomitant medications and adverse events will start after the signing of the ICF through study completion.

